7.2.2.2 Missing items within PRO data

The method of handling missing data for each questionnaire will be based upon the author's recommendation. Details can be found in Section 7.1.3.

7.2.2.3 Concomitant medications definitions and handling of missing or incomplete dates

Should the start date for a medication/procedure be missing or incomplete to the extent that it could be before or after the time of start of study medication, then it will be assumed that the medication/procedure began after the start of study medication (i.e. reported as concomitant medication/procedure). Similarly, if it is not clear whether the medication/procedure start date was on or before the date of entry into the follow-up period, then it will be assumed the medication/procedure began on or before the entry date (i.e. reported as a concomitant medication/procedure) (worst case approach).

For listings of medications, dates will be presented as they have been recorded (missing and partial dates will not be replaced).

7.2.2.4 Definition of treatment-emergent AEs and handling of missing or incomplete dates

In the event of an incomplete onset date, the event will be considered to be treatment-emergent unless the partial onset date information or complete or partial end date confirms onset or end prior to the first dose of study medication date.

For AEs listings, dates will be presented as they have been recorded (missing and partial dates will not be replaced).

8 STATISTICAL METHODS

8.1 General statistical conventions

All statistical procedures will be completed using SAS version 9.4 or higher and ADDPLAN DF 4.0 or later.

8.1.1 Populations for analysis

Demographic and baseline characteristics will be summarised by the Safety population, unless otherwise stated.

Analyses of the primary efficacy endpoint and selected secondary endpoints will be performed on the FAS population and also on the mFAS, PP population and Non-restricted FAS as a sensitivity analysis.

The remaining secondary and exploratory efficacy endpoints will be analysed using the FAS and Non-restricted FAS only.

All safety and tolerability variables will be analysed using the Safety population.

PK data will be analysed using the PK population.

8.1.2 Treatment groups

Statistics will be displayed for the following treatment groups:

- Setrusumab 20 mg/Kg
- Setrusumab 8 mg/Kg
- Setrusumab 2 mg/Kg
- Open Label Setrusumab 20 mg/Kg
- Pooled Setrusumub 20 mg/Kg (where applicable)
- Placebo
- Total: overall (where applicable).

Pooled Setrusumub 20 mg/Kg may only be used for the follow-up analysis.

8.1.3 Descriptive statistics

Continuous variables will be summarised using descriptive statistics including number of non-missing observations (n), means (Mean), standard deviations (SD), minimum (Min), median, and maximum (Max). One additional decimal point for mean and median and 2 additional decimal points for SD will be used.

For categorical variables, summaries will include the number of non-missing observations (n) or the number of patients in the population (N) as applicable, the counts of patients and percentages.

Percentages will be rounded to one decimal place. The number of missing values will be presented as a separate category with no percentage, but only if any missing value is recorded in the data for that summary.

Data in summary tables will be presented on an Observed Cases (OC) basis and summary statistics will only be presented at each visit for which the parameter is scheduled to be collected.

8.1.4 Statistical significance

Unless otherwise stated, all statistical testing will be two-sided and conducted at the significance (alpha) level of 0.05. Two-sided 95% confidence intervals (CIs) will be provided when relevant.

For the primary analysis the LSMeans for each blinded treatment group will be calculated and tested against the null hypothesis of 0 in an a priori hierarchical approach, starting with the highest dose.

For secondary and exploratory endpoints treatment groups will be assessed by pairwise comparisons for secondary efficacy data, and no adjustment for multiplicity will be made.

8.1.5 Definition of Baseline

Unless otherwise stated, Baseline will be the last assessment value before first study dose of study medication. For patients that were randomised to placebo prior to protocol amendment 4.0, assessments taken while on placebo may be utilized for the baseline derivation of each parameter.

For HRpQCT scan parameters baseline assessments maybe collected up to 10 days post the first dose of study medication.

Change from Baseline is defined as (value at assessment date – baseline value).

8.1.6 Visit dates

For each visit, the date recorded by the Investigator in the eCRF will be considered as the visit date in all the algorithms and the listings.

Outputs will include all data collected from screening through to the end of the follow-up period.

8.1.7 Data re-allocation

The following general rules to handle repeated assessments will be considered:

- 12-lead ECG:
 - in case of multiple measurements associated to the same timepoint (e.g. triplicate ECGs), the average value will be considered for HR, PR interval, QRS duration, QT interval and QTcF interval.

8.1.8 Data listings

All the relevant patient data, including those derived and those assessments prior to protocol

amendment 4.0 on the placebo arm, will be presented in individual patient data listings. All listings will be sorted by treatment group, investigational site, patient number, date/time and visit. The patient's sex and age will be stated on each listing. Unless otherwise stated, data listings will be based on all patients randomised.

Unscheduled visit results will be included in date/time chronological order within patient listings, but will not be tabulated.

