9.1. Discontinuation of Study Treatment

Participants may voluntarily discontinue investigational treatment for any reason at any time. If the participant no longer wants to take part in the study, they will be asked to attend an end of treatment visit and 60-day follow-up visit and be discontinued from the study.

The investigator should discontinue investigational treatment of a given participant if, on balance, he/she believes that continuation would be detrimental to the participant's well-being. However, the participant should be followed up to the end of the study and all study procedures should be performed per protocol.

Investigational treatment must be discontinued under the following circumstances and then further steps need to be discussed with the medical monitor:

1. Anaphylactic reaction or other severe systemic reaction to study drug injection
2. Diagnosis of malignancy during study
3. Evidence of pregnancy
4. Absolute corrected QT interval (QTc) corrected using Fridericia's formula (QTcF) is >500 msec and rise from baseline, confirmed by triplicate ECGs, is ≥ 60 msec (Refer to [Section 10.4.3](#))
5. Any of the following confirmed laboratory abnormalities:
 - Renal function values that require discontinuation:
 - Discontinue investigational treatment for a participant if individual serum creatinine increases $\geq 50\%$ compared to baseline (and is considered clinically significant), or in the event of treatment-emergent proteinuria (albumin: creatinine ratio > 300 mg/g or > 30 mg/mmol; protein: creatinine ratio (PCR) ≥ 500 mg/g or > 50 mg/mmol), unless the event is not drug related, or if the risk/benefit assessment supports continuing investigational treatment.

Note: A renal event leading to participant discontinuation should be followed up until event resolution (serum creatinine within 10% of baseline, PCR within 50% of baseline), stabilises or becomes not clinically significant, or is assessed as being chronic.

- Liver laboratory values that require discontinuation
 - Confirmed alanine aminotransferase (ALT) or aspartate aminotransferase (AST) > 5 times the upper limit of normal (ULN) (for more than 2 weeks)
 - Confirmed ALT or AST > 3 times the ULN and confirmed bilirubin total > 2 times ULN (unless elevated bilirubin is related to confirmed Gilbert's syndrome)

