10.4.4. Clinical Safety Laboratory Assessments

- Refer to [Appendix 2](#) for the list of clinical laboratory tests to be performed and to the SoA for the timing and frequency.
- The investigator must review the laboratory report, document this review, and record any clinically relevant changes occurring during the study in the AE section of the eCRF. The laboratory reports must be filed with the source documents. Clinically significant abnormal

laboratory findings are those which are not associated with the underlying disease, unless judged by the investigator to be more severe than expected for the participant's condition.

- All laboratory tests with values considered clinically significantly abnormal during participation in the study or within 60 days after the last dose of study treatment should be repeated until the values return to normal or baseline. If such values do not return to normal/baseline within a period of time judged reasonable by the investigator, the etiology should be identified and the sponsor notified.
- All protocol-required laboratory assessments, as defined in [Appendix 2](#), must be conducted in accordance with the laboratory manual and the [SoA](#).
- If laboratory values from non-protocol specified laboratory assessments performed at the institution's local laboratory require a change in participant management or are considered clinically significant by the investigator (e.g., SAE or AE or dose modification), then the results must be recorded in the eCRF.

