
NOTES:
 
¹ Details of liver chemistry stopping criteria and required actions and follow-up assessments after liver stopping or monitoring event are given in Section 9.1. All events of ALT $\geq 3 \times$ ULN and bilirubin $\geq 2 \times$ ULN (>35% direct bilirubin) or ALT $\geq 3 \times$ ULN and international normalised ratio (INR) >1.5, if INR measured which may indicate severe liver injury (possible Hy's Law), must be reported as an SAE (excluding studies of hepatic impairment or cirrhosis).
 
² Local urine testing will be standard for the protocol unless serum testing is required by local regulation or IRB/IEC.
	

Investigators must document their review of each laboratory safety report.

Laboratory/analyte results that could unblind the study will not be reported to investigative sites or other blinded personnel until the study has been unblinded.

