7.1.4.4 Potential Hy's Law Criteria

Patients will be deemed as meeting potential Hy's law Criteria if their ALT or AST > 3x ULN and bilirubin > 2 x ULN at the same visit.

Further assessment to determine that no other reason can be found to explain the combination of increased aminotransferase and serum total bilirubin, such as viral hepatitis, alcohol abuse,

ischemia, pre-existing liver disease, or another drug capable of causing the observed injury will be conducted.

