8.6.2.1 Liver Function

The number and proportion of patients with laboratory values for liver function and enzymes of clinical concern as follows will be presented descriptively by treatment group:

Parameter	Level for clinical concern
ALT	> 1.5 times the upper limit of the normal range (ULN) > 2xULN > 3xULN > 5xULN > 10xULN
AST	> 1.5xULN > 2xULN > 3xULN > 5xULN > 10xULN
Bilirubin Total	> 2xULN > 3xULN
ALT/AST and Bilirubin Total	ALT/AST > 3xULN and Bilirubin Total > 2xULN (assessments to occur at the same visit)

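### SAP 8.1.8 keeps unscheduled results out of every table, so the liver threshold and potential Hy's law counts can be understated but never overstated

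*SAP*

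**What the plan says.** **What is tabulated.** SAP 8.1.8: "Unscheduled visit results will be included in date/time chronological order within patient listings, but will not be tabulated". SAP 8.1.3 points the same way: "summary statistics will only be presented at each visit for which the parameter is scheduled to be collected". The only rule for repeated assessments, in SAP 8.1.7, concerns ECGs.

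**What the liver table counts.** SAP 8.6.2.1 presents "The number and proportion of patients with laboratory values for liver function and enzymes of clinical concern" by treatment group, with ALT and AST rows from 1.5 to 10 times ULN and bilirubin rows at 2 and 3 times ULN. The combined row reads "ALT/AST > 3xULN and Bilirubin Total > 2xULN (assessments to occur at the same visit"). SAP 7.1.4.4 defines potential Hy's law in the same way: "ALT or AST > 3x ULN and bilirubin > 2 x ULN at the same visit". Neither section mentions a worst value per participant or unscheduled samples.

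**What the protocol generates.** Protocol 10.4.4 says that clinically significant abnormal values "should be repeated until the values return to normal or baseline". Section 10 of the protocol allows unscheduled samples for safety. Protocol 9.1 bases liver discontinuation on confirmed values. One rule is ALT or AST "> 5 times the upper limit of normal (ULN) (for more than 2 weeks"). The other is confirmed ALT or AST above 3 times ULN with confirmed total bilirubin above 2 times ULN, with no same-visit condition.

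**The concern.** The protocol calls for repeat liver tests, and the SAP then keeps any that are unscheduled out of the one table that reports liver results as multiples of ULN. A participant's peak, the sample that confirms an elevation, or the sample on which bilirubin first joins a raised ALT may all fall outside the count. Protocol 6.5 selects the dose on HRpQCT results and safety, and the arms are planned at 25 participants, so a small number of missed threshold crossings could change how the dose groups compare on liver safety.

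**Working it through.** The plan gives no figure on this point to reproduce. The check has four parts.

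**1. Spacing of scheduled samples.** Inputs: safety laboratory visits at baseline and Months 1, 2, 3, 6, 9, 12/EOT, 14, 18 and 24 (Protocol Schedules of Activities; SAP 8.6.2); a month is 28 days (Protocol 6.1); visits are ±4 days, so a gap can vary by ±8 days.

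| Interval | Gap (days) | With visit windows |
|---|---|---|
| Baseline to Month 3, each step | 28 | 20–36 |
| Months 3–6, 6–9, 9–12 | 3 × 28 = 84 | 76–92 |
| Months 12–14 | 2 × 28 = 56 | 48–64 |
| Months 14–18 | 4 × 28 = 112 | 104–120 |
| Months 18–24 | 6 × 28 = 168 | 160–176 |

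The three long treatment-period gaps total 3 × 84 = 252 of 12 × 28 = 336 days, or 75%. Up to Month 3, the next scheduled sample could serve as confirmation. After Month 3 it is about 11 to 13 weeks away, so prompt confirmation needs an unscheduled sample.

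**2. Direction of the error.** Let S be a participant's scheduled samples and U the unscheduled ones. The table counts the participant if max(S) exceeds the threshold. Since max(S ∪ U) ≥ max(S), everyone counted on S is also counted on S ∪ U, but not the reverse. Likewise, any same-visit ALT/AST and bilirubin pair within S is also a pair within a time window on S ∪ U. Relative to a count on all samples, the planned counts are therefore equal or lower, never higher.

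**3. Two hypothetical cases against the text.**

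- ALT is 2.5 × ULN at Month 6, 6 × ULN on a repeat, and still 6 × ULN on a second repeat more than 2 weeks later. The first rule in Protocol 9.1 is met. The > 5 × ULN row counts this participant only if a scheduled sample, such as EOT, is taken while ALT is still above 5 × ULN. Otherwise the case can stay in the > 2 × ULN row.
- ALT is above 3 × ULN at a scheduled visit with normal bilirubin, and bilirubin first exceeds 2 × ULN on a repeat a week later. The pair is missed because the repeat is unscheduled. If ALT has fallen to 3 × ULN or below by then, the same-visit condition would exclude it as well.

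**4. The liver criteria side by side.**

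| Source | Transaminase | Second condition | Other |
|---|---|---|---|
| Protocol 9.1 (stopping) | ALT or AST > 3 × ULN | Total bilirubin > 2 × ULN | Both confirmed; Gilbert's exception |
| Appendix 2 note 1 (SAE) | ALT ≥ 3 × ULN | Bilirubin ≥ 2 × ULN, or INR | > 35% direct bilirubin; "international normalised ratio (INR) >1.5, if INR measured which may indicate severe liver injury" |
| SAP 7.1.4.4 (count) | ALT or AST > 3 × ULN | Bilirubin > 2 × ULN | Same visit; no INR |

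A confirmed AST-only elevation with raised bilirubin falls under the first and, if at the same visit, the third, but not the second. ALT with INR above 1.5 and normal bilirubin falls under the second only.

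**The case against.** The strongest reply is that little is lost.

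- **First elevations count.** An elevation found at a scheduled visit enters the single-parameter rows. This stands; what can be lost is the peak, the confirmation, or a combination first met off schedule.
- **Early stoppers have further scheduled samples.** Under the protocol synopsis they attend an end-of-treatment visit and a 60-day follow-up visit, and SAP 8.6.2 treats EOT and Month 14 as scheduled laboratory times. These may catch some cases, but not reliably the peak.
- **Other tables show the event by dose group.** Clinically relevant laboratory changes are recorded as AEs, and possible Hy's law events under Appendix 2 are SAEs. SAP 8.6.1 tabulates SAEs, severe TEAEs and AEs leading to permanent discontinuation; SAP 8.2 tabulates reasons for discontinuation. This also stands. A reader might infer that a participant stopped for a liver reason vanishes from the safety results by dose, and the documents do not support that. Those tables report coded events and reasons, however, not ULN multiples.
- **SAP 8.1.6 says outputs cover all data from screening to the end of follow-up.** That describes the period covered and does not override the specific exclusion in 8.1.8.
- **The DMC reviews unblinded safety data** under its own charter and SAP, which are not available here. That may help monitoring but does not change the planned liver table.
- **The three liver criteria serve different purposes** and need not be identical. This is fair, and is a reason to ask for an explanation rather than to call any of them wrong.

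**Conclusion.** The concern holds as a gap in one safety table. Followed as written, the SAP can understate the liver threshold and potential Hy's law counts and cannot overstate them relative to all samples. By how much cannot be computed, because the documents do not say how often unscheduled samples are taken or how long elevations last. For scale only, one missed participant is 1/25 = 4 percentage points of an arm.

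Three stronger readings are not supported:

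- **A loss of half to two thirds.** Dividing an assumed duration by the 84-day gap gives 28/84 = 33% and 42/84 = 50% caught by a scheduled sample. The durations have no source in the documents, and the ratio measures how often participants are monitored, not what the tabulation rule removes. It also applies only within the long gaps. Over the full treatment period the same assumptions give (252 × 56/84)/336 = 50% and (252 × 42/84)/336 = 37.5% meeting no scheduled sample.
- **A single repeat at 6 × ULN meets the stopping rule.** It does not: Protocol 9.1 requires confirmation and more than 2 weeks.
- **Potential Hy's law is assessed at one visit only.** The SAP requires both elevations at the same visit, and any such visit qualifies.

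The conclusion assumes that 8.1.8 is programmed literally and that repeats after Month 3 are mostly drawn off schedule.

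**What to change.** In the SAP, before unblinding:

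1. Limit the exclusion in 8.1.8 to by-visit descriptive statistics.
2. In 8.6.2.1, count each participant by the worst value after first dose from all scheduled and unscheduled samples. State whether local-laboratory values entered in the eCRF under Protocol 10.4.4 are included, and which ULN applies to them.
3. In 7.1.4.4, assess ALT/AST with bilirubin on all samples within a prespecified time window, and also report the subset meeting both criteria on the same sample. The window is needed because unrestricted peak-against-peak pairing could join an early ALT to a much later, unrelated bilirubin value.

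Separately, reconcile the liver criteria in Protocol 9.1, Appendix 2 note 1 and SAP 7.1.4.4, or explain why they differ on AST, on > versus ≥, on direct bilirubin and on INR.

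The cost is SAP wording and minor programming; repeat and unscheduled results are already to be listed. The drawback for the sponsor is that the counts may look slightly less favourable.

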8.2 Patient disposition

All patients who provided informed consent will be included in a summary of patient disposition. The number of patients screened, the number of screen failures, the frequency of patients randomised (by treatment group and overall), the frequency and percentage of patients in the Safety population, in the FAS population, in the mFAS population, in the Non-restricted FAS population, in the PP population and in the PK population (by treatment group and overall) will be summarised.

Patient disposition information will be summarised by treatment group and overall. The number of patients completing and withdrawing the treatment period and follow-up period will be tabulated in the study disposition table which will also include the reasons for treatment discontinuation and early withdrawal of the patient as reported on the eCRF.

Finally, the reasons for screen failure as reported on the eCRF will be tabulated.

A listing will include the randomisation/kit numbers, randomisation date/time and study disposition data (using the enrolled population).

8.3 Protocol deviations

The number of patients excluded from FAS, mFAS, Non-restricted FAS, Safety, PP and PK populations and reasons for exclusion will be summarised by treatment group and overall.

All key protocol deviations identified will be summarised by treatment group and overall.

In addition all protocol deviations will be listed based on data recorded on the eCRF and/or protocol deviation Logs (from CTMS).

8.4 Demographics and baseline characteristics

No formal comparison between treatment regimens on demographics and baseline characteristics will be conducted.

8.4.1 Demographics

Demographics including age, sex, race, ethnicity, weight, height, BMI and child-bearing potential will be listed and summarised using descriptive statistics for continuous variables and tabulated for categorical variables. Summary will be produced using the Safety Population.

8.4.2 Fracture/OI history

Fracture/ OI history including the number patients experiencing any fracture within the last 2 years (5 years from protocol amendment 4.0), time since last fracture (months), description of fracture (location), fracture anatomical location, percentage compression (vertebral only), evidence of interval healing, fracture history patient reported (Y/N), OI Type and COL1A1/COL1A2 testing (Y/N) will be summarised by treatment group and overall using the safety population.

8.4.3 Medical and Physical Aids History

A summary of Medical and Physical Aids history will be presented by medical history code, system organ class (SOC) and preferred term (PT), by treatment group and overall using Medical Dictionary for Regulatory Affairs® (MedDRA) using the Safety population.

8.4.4 Prior, Concomitant and Follow-up medications

Prior and concomitant medications will be coded using the World Health Organization (WHO) Drug Dictionary.

Prior, concomitant and follow-up medications will be summarised by Anatomical Therapeutic Chemical (ATC) classification level 4 and Preferred Name by treatment group and overall for the Safety population.

8.4.5 Concomitant Procedures/Physical Aids

All concomitant Procedures and Physical Aids will be coded using the World Health Organization (WHO) Drug Dictionary and will be presented by medication class, treatment group and overall.

